13.6.3 Clinical laboratory evaluations

Safety laboratory data (haematology, clinical chemistry, and urinalysis) will be summarised by visit and treatment. All laboratory data will be included in the data listings. In addition, a separate listing of laboratory data for subjects with clinically significant abnormal results will be prepared.

13.6.4 Other safety measures

Vital signs (body temperature, respiratory rate, heart rate, and blood pressure) will be summarised by baseline and treatment overall and for each treatment within the treatment sequence. Changes over time in vital signs will be summarised.

Physical examination data will be listed only.

The number and percentage of subjects receiving concomitant medications will be tabulated overall and by medication received.

13.7 Analysis of pharmacokinetic data

The following pharmacokinetic parameters will be derived from the plasma concentrations of LAT8881 and metabolites, where practicable:

C_{max} Maximum plasma LAT8881 concentration

T_{max} Time to maximum plasma LAT8881 concentration

AUC_{0-t} Area under LAT8881 concentration time curve from dosing to the last observed concentration

value above the limit of quantification

AUC_{0-inf} Area under LAT8881 concentration time curve from dosing to the last observed concentration

value above the limit of quantification, extrapolated to infinity

T_{1/2} Terminal elimination half life

AUC_{0-t} will only be calculated if there are at least three quantifiable data points.

 $T_{1/2}$ will only be determined if there are at least three quantifiable elimination phase data points.

Plasma LAT8881 values below the limit of quantification will be labelled as (BLQ) in the plasma LAT8881 data listings and set to zero if recorded pre-dose.

The change in PK parameters on the last day of treatment compared with those determined after the initial dose will be investigated using a paired t-test. The mean change after repeated dosing will be presented with the corresponding 95% confidence interval and p value.

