5.1 Overall study design

This is a randomised, placebo-controlled, double-blind, crossover, multi-site, Phase IIa study to investigate the efficacy and safety of oral LAT8881 in neuropathic pain. The overall study design is shown in Figure 4. Details of the procedures during each phase are described in Section 8.

The pharmacokinetics (PK) of LAT8881 will be investigated on Days 1, 28, 50 and 77 in 15 subjects (PK subjects) at Australian sites. Quantitative sensory testing (QST) will be performed in up to 20 subjects (QST subjects) before the first dose on Days 1 and 50 and after the morning dose on Days 28 and 77. PK subjects will not participate in QST measurements and QST subjects will not participate in PK analyses.

[figure not shown]

Figure 4: Overall study design for LAT-NP-001

Potential subjects will be required to provide written informed consent prior to any study-specific screening procedures being performed. Screening assessments will be performed from Day -28 to Day -1. Subjects deemed likely to be eligible for the trial will be given access to a diary during Screening Stage 1 and training on how to complete it from Days -7 to -1 inclusive (Screening Stage 2, first baseline period). These diary results will be reviewed on Day 1 to confirm that the subject is eligible for the study.

On Day 1, after the first baseline period, eligible subjects will be enrolled and randomised to LAT8881 or placebo. They will receive the investigational medicinal product (IMP) twice daily for four weeks (Days 1 to 28). On the morning of Day 28 they will return to the clinic for their end of first treatment visit and will take an IMP capsule in the morning during their clinic visit. They will take their final IMP dose for this treatment period in the evening.

The first treatment period will be followed by a washout period of two weeks (Days 29 to 42 inclusive) and then a second baseline period of one week (Days 43 to 49 inclusive). Over these days (i.e. Days 29-49 inclusive) subjects will not take any IMP.

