10.2.2 Pharmacokinetics

Blood samples (4 mL) will be taken pre-dose (within 30 minutes of dosing) and 2, 5, 15, 30, 60 minutes, 2, 4 and 6 hours after IMP ingestion. Blood samples will be obtained by direct venepuncture or via an indwelling cannula. Samples taken 2, 5 and 15 minutes after dosing should be within +/- 1 minute of the stated time, samples at later time points within +/- 5 minutes of the stated time.

Blood samples

will be kept on ice immediately after collection to minimise degradation and centrifuged within 60 minutes post-collection in a pre-cooled (refrigerated) centrifuge. The resulting PK plasma samples will be transferred to clean, pre-labelled polypropylene tubes and stored frozen prior to analysis. Pre-dose samples will be centrifuged separately prior to dosing.

Further details will be provided in the Laboratory Manual.

Samples will be analysed under GLP conditions by

An initial

batch of 25% of the total number of samples will be tested. If all samples tested are below the limit of quantification of the assay, further analyses will not be undertaken until the sensitivity of the assay is significantly increased.

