13.1 General considerations

The statistical analysis principles described below will be supplemented by a comprehensive statistical analysis plan (SAP) which will be finalised before the database is locked. This will contain details of methods for handling missing data, early withdrawals, and potential covariates. Any changes to the statistical analysis plan will be described and justified in the final report.

The descriptive summary for the categorical variables will include counts and percentages. The descriptive summary for the continuous variables will include number of subjects (n), means, medians, standard deviations, and minimum and maximum values. Pharmacokinetic measures will be analysed as for continuous variables. All data will be listed for all subjects. All confidence intervals (CIs) will be 95%, unless stated otherwise. All statistical analyses will be performed using SAS unless otherwise stated.

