10.16.3 Baseline NPRS Variability

Baseline NPRS mean score will be recorded along with the respective standard deviations for each subject. Subjects will be sorted by SD (highest to lowest) for the first baseline results. Subjects having variability in quartiles 1 to 3 (i.e., 75%), will be flagged for analysis (i.e. subjects with the 25% most variable baseline results for treatment period 1 will be excluded).

11 Statistical Analyses

Summaries will be based on treatment sequence for the following:

- Subject Disposition
- Demographic and Baseline Characteristics
- Prior Medications
- Medical / Surgical History

“Total” columns will be included in these summaries. For all other analyses, summaries will be based on treatment overall and within study periods.

Following conventions will be used for the choice of treatment sequence / group in summaries:

- FAS Population – Planned treatment sequence / group
- Safety Population – Actual treatment sequence / group
- Per-protocol Population – Actual treatment sequence / group
- ██████████ Actual treatment sequence / group

Analysis of Plasma concentration and Pharmacokinetic data will be done separately, and not included in this Statistical Analysis Plan.

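### Protocol 13.7 compares last-day with first-dose PK, Tmax included, by a paired t-test on the mean change; a log-scale ratio, and ranks for Tmax, would serve better on the same data

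*Protocol*

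**What the plan says.** Protocol 13.7 lists Cmax, Tmax, AUC0-t, AUC0-inf and T1/2. One sentence covers them all: the change between the initial dose and the last treatment day "will be investigated using a paired t-test". The next fixes the output: "The mean change after repeated dosing will be presented with the corresponding 95% confidence interval and p value". Tmax appears in the list simply as "Time to maximum plasma LAT8881 concentration", with no method of its own.

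Protocol 13.1 adds "Pharmacokinetic measures will be analysed as for continuous variables", and the descriptive statistics it names for continuous variables are n, mean, median, SD, minimum and maximum. Geometric means, log transformation and ratios are not mentioned in either section.

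PK is measured "in 15 subjects (PK subjects) at Australian sites" (Protocol 5.1), with blood drawn before dosing and "2, 5, 15, 30, 60 minutes, 2, 4 and 6 hours after IMP ingestion" (Protocol 10.2.2).

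The SAP, in the opening text of Section 11, says: "Analysis of Plasma concentration and Pharmacokinetic data will be done separately, and not included in this Statistical Analysis Plan". Section 12 repeats this. Neither section changes the test in Protocol 13.7, which is therefore the only PK test in the two documents.

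**The concern.** Accumulation is naturally a multiple of first-dose exposure. A mean difference in concentration units is dominated by the subjects with the highest exposure and does not give the reader the last-day/first-dose ratio. With so few pairs, a skewed distribution of differences also widens the t interval and lowers power.

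Tmax can take only the scheduled sampling times. These run from 2 minutes to 6 hours at very uneven spacing, so a change between 4 and 6 hours counts for far more in a mean than a change between 5 and 15 minutes.

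What is at stake is a clear and efficient answer on whether exposure changes over four weeks of dosing. The primary NPRS analysis is not affected.

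**Working it through.** **No PK figure to reproduce.** The documents give no CV, correlation, expected ratio or power for this comparison. The variability and ratio values below are assumptions, shown over a range.

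**Number of pairs.** There are 15 PK subjects (Protocol 5.1), and each takes LAT8881 in one period only, so there are at most 15 LAT8881 pairs. With the 20% dropout of Protocol 13.2: 15 × (1 − 0.20) = 12. Unquantifiable samples could reduce this further.

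**Model for Cmax and AUC.** Lognormal values with between-subject SD √ln(1 + CVb²) and within-subject SD σw = √ln(1 + CVw²) on the log scale, and the true last-day/first-dose ratio applied as a multiplier. Tests are two-sided at 5%, matching "All confidence intervals (CIs) will be 95%, unless stated otherwise" in Protocol 13.1. The paired t-test on untransformed values was simulated (40,000 replicates per setting).

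**Log-scale power in closed form.** Subject effects cancel in the log difference, whose SD is σw√2. Noncentrality = ln(ratio) × √n / (σw√2), on n − 1 degrees of freedom. Example with CVw = 40%, ratio 1.5, n = 15:
- σw = √ln(1.16) = 0.385, so the SD of the difference is 0.545
- noncentrality = 0.4055 × 3.873 / 0.545 = 2.88
- power = 76.4% (simulations gave 76% to 77%)

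**Power at n = 15:**

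| CV between/within | Ratio 1.5, untransformed | Ratio 1.5, log | Ratio 2, untransformed | Ratio 2, log |
|---|---|---|---|---|
| 30/20% | 99.8% | 99.9% | ≥99.8% | ≥99.8% |
| 50/30% | 87% | 94% | ≥99.8% | ≥99.8% |
| 60/40% | 62% | 76% | 96% | 99.5% |
| 80/50% | 40% | 59% | 80% | 96% |
| 100/60% | 26% | 46% | 61% | 89% |

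At a ratio of 1.1 neither scale has useful power: 21.7% against 23.4% at 30/20%, and 4.3% against 7.1% at 100/60%.

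**Power at n = 12, ratio 1.5:** 51% against 65% (60/40%), 31% against 48% (80/50%), 20% against 37% (100/60%).

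**A second parametrisation.** With equal CV on both days, correlation 0.5, n = 15 and ratio 1.5, untransformed against log power is 99.8% against 99.9% (CV 30%), 81.9% against 87.2% (50%), 41.8% against 54.5% (80%) and 20.5% against 33.5% (120%). The direction is the same.

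**Type I error.** With no true change and n = 15, the untransformed test rejects in about 3% to 5% of studies and the log test in about 5%.

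**Tmax.** Simulated on the protocol's sampling grid with n = 15 (assumed centre 0.5 h, log-SD 0.8, correlation 0.5). For a shift of 0.5 on the log scale, power is 40.9% for the t-test and 48.7% for the signed-rank test. With no shift the rejection rates are 3.9% and 5.0%.

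**The case against.** The strongest reply is that the untransformed scale is inferred from silence. Protocol 13.1 offers principles to be supplemented later, and the SAP sends PK to a separate analysis that may already work on logs. That is fair, and the reading stays an inference. It is still the natural one: the output is a mean change, PK measures are treated as ordinary continuous variables, and nothing in either document says otherwise.

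A reader might also infer that a stated secondary objective is compromised. The documents do not support that. Protocol 4.2 asks only for the pharmacokinetics after a single dose and after four weeks; Protocol 9.4 lists parameters on each occasion; the synopsis describes PK as listed and summarised descriptively. The formal comparison appears only in 13.7, without a hypothesis or power target.

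Nor is the test invalid. It is slightly conservative, a mean change with its interval can be interpreted, and full listings would let a reader derive ratios. The Tmax difference is modest under the assumed inputs.

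Finally, the power loss is small at low variability: under one percentage point at 30/20%. It becomes material only with high CVs and real accumulation, and the documents establish neither. This limits the size of the point. The missing ratio remains at any CV.

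**Conclusion.** The point stands as a minor, low-cost improvement. As written, Protocol 13.7 yields no accumulation ratio, applies a mean-based test to Tmax, and can lose power on skewed Cmax and AUC. At 15 pairs and a ratio of 1.5 the loss runs from negligible (30/20%) through about 7 points (50/30%) and 14 points (60/40%) to about 20 points (100/60%). These figures rest on lognormal data, complete quantifiable pairs, and assumed CVs and ratio.

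Fifteen pairs is a best case. Protocol 10.2.2 allows for a first assay batch that is entirely below the limit of quantification, and 13.7 derives parameters only where practicable, with AUC0-t needing three quantifiable points. False-positive risk is not raised, and nothing here touches the primary analysis.

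**What to change.** In Protocol 13.7 and in the separate PK plan:

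- Analyse log Cmax and log AUC by a paired t-test on the LAT8881 period only. Back-transform to the last-day/first-dose geometric mean ratio with its 95% CI.
- Use the same AUC interval on both days. AUC0-t ends at each subject's last quantifiable sample, and sampling stops at 6 hours, so unequal intervals would distort the ratio.
- State how a pair is handled when either value is unquantifiable, since its log is undefined. The present rule sets values to zero only for pre-dose samples. Report the number of pairs used for each parameter.
- Compare Tmax by the signed-rank test with a median difference.

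The cost is wording only, with no new data, samples or visits. The edit to 13.7 would go through the amendment procedure in Protocol 14.1.4. Fixing the scale before treatment codes are released also removes a later choice.

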13.8 Analysis of exploratory endpoints

Exploratory analyses will be undertaken to determine the relationship between change in mean NPRS from baseline to the end of four weeks treatment and baseline parameters, such as the clinical diagnosis (PHN or DPN) and baseline QST parameters. The effect of treatment on changes in QST parameters from baseline to the end of four weeks treatment will also be analysed.

The effect of the variability in NPRS scores within the first baseline period on the ability to detect a treatment difference will be examined.

The relationship between plasma LAT8881 and NPRS in PK subjects will also be investigated.

The approaches to these investigative analyses will be detailed in the statistical analysis plan.

14. Study management

14.1 Regulatory and ethical considerations

14.1.1 Regulatory compliance and ethical conduct

This study must be conducted in compliance with the study protocol, the requirements and obligations of the International Conference on Harmonisation (ICH) and Good Clinical Practice (GCP) guidelines, Integrated Addendum to ICH E6(R1): Guideline for Good Clinical Practice E6(R2),¹ the World Medical Association Declaration of Helsinki²³ and its amendments and all applicable local guidelines, laws and regulations.

Investigators and other site personnel will undergo appropriate study-specific training during the study site initiation visit. Before initiation of the study at the site(s), the written approval / favourable opinion of the local and/or national independent Ethics Committee(s) and relevant Health Authority(ies) will be sought and obtained.

14.1.2 Ethics Committee review

Prior to the initiation of the study, the protocol and associated documentation (including all materials used to recruit subjects for the study) must be given a favourable opinion by an Ethics Committee (EC). A copy of this written approval and any correspondence with the EC will be provided to the sponsor.

The investigator must obtain approval from the sponsor before potential subjects can undergo any studyspecific screening procedures.

The investigator will comply with any additional requirements imposed by the EC. The investigator must submit progress reports to the EC according to local regulations and guidelines. The investigator must also provide their EC with any reports of SAEs from the study site in accordance with the EC's requirements and timelines.

14.1.3 Informed consent process

The investigator will ensure that the subject is given full and adequate oral and written information about the nature, purpose, possible risks and potential benefits of the study. Subjects must also be notified that they are free to discontinue from the study at any time. The subject should be given the opportunity to ask questions and should be allowed time to consider the information provided.

The subject's signed and dated informed consent must be obtained before conducting any procedure specifically for the study. The investigator must store the original, signed ICF with the subject's medical records. A copy of the signed and dated ICF must be given to the subject.

Subjects who are incompetent and unable to freely provide informed consent and subjects who are unable to read or speak English without the assistance of an interpreter will not be invited to participate in the study.

If new information arises during the study that may affect the safety of the subjects, the protocol and ICF will be amended as appropriate and submitted to the EC as outlined in Section 14.1.4. Following approval by the EC, subjects will be advised by letter of any safety related updates that may impact during the post-study period and be invited to discuss any concerns with the investigator. When applicable, subjects may be requested to re-consent to ongoing their participation in the study.

14.1.4 Protocol amendments

Modification of the signed, EC-approved protocol must not be changed without the agreement of the sponsor. If it is necessary for an EC-approved study protocol to be amended, the relevant EC and, if required, the local regulatory authority must be informed and asked for its opinion as to whether a reevaluation of the ethical aspects of the study is necessary. In the UK, a substantial amendment to the

protocol will be submitted to the Medicines and Healthcare Products Regulatory Agency for approval.

The investigator must not implement any deviation from, or change to the protocol, without agreement by the sponsor and prior review and documented approval/favourable opinion of the amendment from the relevant EC, except where it is necessary to eliminate an immediate hazard to study subjects, or where the change(s) involve(s) only logistical or administrative aspect(s) of the study, for example, change in monitor(s) or change of telephone number(s).

If a protocol amendment requires a change to the Participant Information Sheet (PIS) or Informed Consent Form (ICF), approval of the revised PIS and ICF by the sponsor and EC is required before the updated document can be used.

Following approval, the sponsor (or delegate) will distribute new versions of amended documents (e.g. protocol, PIS, ICF) to the site.

14.1.5 Protocol deviations

No deviations from or changes to the protocol will be implemented without documented approval from the EC of an amendment, except where necessary to eliminate an immediate hazard(s) to study subjects or when the change(s) involves only logistical or administrative aspects of the study.

Any deviations from or changes to the protocol which were implemented to eliminate an immediate hazard and the proposed amendment, if appropriate, should be submitted to the EC for review and approval as soon as possible.

Should any protocol deviation occur, it must be reported to the study monitor as soon as is reasonably practical. If a major protocol deviation occurs, the investigator must notify the sponsor and the appropriate EC as soon as possible or as per local requirements.

All instances of noncompliance with the requirements of the Study Protocol will be captured in a Protocol Deviation Log. The deviation and the reason for its occurrence must be documented, reported to the relevant EC (if required) and included in the clinical study report.

14.2 Quality control and quality assurance

14.2.1 Training of staff

Each individual involved in the study must be qualified by education, training and experience to perform his or her respective tasks.

Site staff may be trained at investigator meetings and initiation visits by the sponsor or their designees.

14.2.2 Study monitoring

The study will be independently monitored in accordance with ICH GCP¹, and applicable local regulations.

Before the start of the study, a study monitor appointed by the sponsor will evaluate the investigational site to ensure facilities are adequate and to discuss responsibilities with the site staff with regards to following the protocol and regulatory and ethical requirements.

During the study, the study monitor will regularly visit the site to monitor and confirm protocol, regulatory and ethical adherence, confirm data accuracy and provide information and support as needed.

The investigator is responsible for maintaining source documents. The investigator must agree to allow the study monitor direct access to all relevant documents at each monitoring visit, including electronic medical records, and to allocate their time and the time of their staff to the study monitor to discuss findings and any relevant issues.

Site staff will be provided with contact details for the study monitor and back-up persons in the event they have queries or require assistance.

14.2.3 Data management and quality control

The sponsor (or delegate) will be responsible for activities associated with the data management of this study. This will include setting up a database and data transfer mechanisms, along with appropriate validation of data and resolution of queries.

Data generated within this clinical study will be handled according to the relevant SOPs of the sponsor and/or their delegate(s). An electronic CRF (eCRF) will be created by the data management group for recording of the required data and integration into the study database. All data (including electronically available data, i.e. eCRF and laboratory data) will be integrated into a validated Data Management System with full audit trail capability (i.e. a computerised log of all subsequent changes to the data will be recorded). Automated checks will be made against the data to ensure completeness and consistency. The database and check programs will be validated before implementation. AEs will be coded using MedDRA (Version 20.0 or later) and medications will be coded using the current version of the WHO Drug Dictionary.

Missing or inconsistent data will be queried via system generated queries to the investigator for clarification. Subsequent modifications to the database will be documented.

Data collection and entry into the eCRF will be completed by authorised study site personnel designated by the investigator. Appropriate training and security measures will be completed with the investigator and all authorised study site personnel prior to the study being initiated and any data being entered for any study subjects.

The eCRFs should always reflect the latest observations on the subjects participating in the study; therefore, the eCRFs are to be completed as soon as possible during or after the subject's visit. The investigator must verify that all data entries in the eCRFs are accurate and correct. If some assessments are not done, or if certain information is not available or not applicable or unknown, this should be indicated in the eCRF. The investigator will be required to sign off on the final clinical data.

During the study the study monitor will review the eCRFs and evaluate them for completeness and consistency. The eCRF will be compared with the source documents to ensure that there are no discrepancies. All entries, corrections and alterations are to be made by the investigator or designee.

The study monitor cannot enter data into the eCRFs. If corrections are needed, the responsible study monitor or data manager will raise a query and the appropriate investigational staff will be required to provide an answer. All queries and resultant data changes will have an electronic audit trail, meaning that the name of the investigational staff responding to the query, time and date stamp are captured.

The eCRF is considered a data entry form and should not constitute the original, or source document, unless otherwise specified. Source documents are documents used by the investigator or study site that relate to the subject's medical record, that verify the existence of the subject, the inclusion and exclusion criteria and all records covering the subject's participation in the study. They include, but are not limited to, laboratory reports, hospital records, subject files, etc.

eCRFs will be completed for subjects who have signed the ICF, are eligible for this study and have been enrolled in the study.

